## **8.4 STATISTICAL ANALYSIS OF THE SECONDARY ENDPOINTS**

Secondary study endpoints will include:

- Complete metabolic response rate at the bi-weekly visits.
- Combined complete and partial metabolic response rate: partial response defined as both a decrease of at least 50% in FGF23 and an increase of at least 50% in phosphorus in the plasma at the bi-weekly, and 12-week follow-up visits.
- Biochemical measures of disease including plasma concentrations of FGF23, mineral panel, 1,25-(OH)2-Vitamin D, alkaline phosphatase, tubular reabsorption of phosphate, TRP, and TmP/GFR measured every 2 weeks.
- Eight quality of life domains from the RAND SF-36 survey measured at baseline and every 4 weeks.
- PROMIS survey measured at baseline and every 4 weeks
- Strength testing measured at baseline and every 4 weeks
- Six-minute walk test assessed at baseline, 24 weeks and 36 weeks.
- Radiographic evidence of TIO (in subjects with measurable tumor burden).

All analyses on the secondary endpoints will be performed on both the intent-to-treat and the per protocol populations.

Similar to the primary analysis, the complete response rate will be estimated with its exact 95% confidence limits, but at each bi-weekly sampling visit. The combined complete and partial response rate will be summarized as percent with its exact 95% confidence limits at every bi-weekly visit but with the 12-week follow-up visit rate of primary interest. Patients that for any

*Abbreviated Title: BGJ398 in TIO*

*Version Date: 21MAY2019*

reason are missing their response status will be counted as failures with respect to achieving complete or partial response.

The biochemical measure of disease secondary endpoints will be analyzed using repeated measures mixed models with the contrast of primary interest between the baseline and the 12-week follow-up visit. Additional post hoc comparisons with corrections for multiple comparisons will compare the measures at the end of each cycle to baseline. Of primary interest will be the reduction of FGF23 concentrations, the increase in both plasma phosphorus and 1,25-OH2-vitamin D, and the other biochemical parameters. These concentration endpoints will be log-transformed if appropriate. The muscle-strength testing, SF-36, and PROMIS will also be analyzed using repeated measures mixed models similarly to the biochemical measures of disease. Patients without baseline values for a particular biochemical measure will be excluded from the analysis. Missing values other than baseline measures will be adjusted-for within the repeated measures, mixed model using restricted maximum likelihood techniques.

Radiographic evidence of TIO will be summarized in patient listings.

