#### 1.1.2 Secondary Objective:

- To evaluate the effects of BGJ398 on:
  - o mineral homeostasis
  - o quality of life
  - o muscle strength.
- To evaluate the effects of BGJ-398 on radiographic evidence of TIO.

**Table 1** summarizes the primary, secondary and exploratory objectives tagged with the associated endpoints and evaluation criteria:

	Objective	Endpoint Measures
Primary	Complete metabolic response	Normalization of blood phosphate and FGF23 off study drug
Secondary/Exploratory	Pharmacodynamics of mineral homeostasis response to BGJ398 in TIO	Changes in FGF23 (intact and C-terminal), Phosphorous, 1, 25 (OH) 2 vitamin D; TRP, TmP/GFR
	Effects on quality of life	Standardized measures of QoL
	Effects on muscle strength	Standardized muscle strength testing
	Effect on radiographic evidence of TIO	Changes in clinically-indicated FDG-PET/CT, octreotide SPECT/CT, or  Ga-DOTATATE PET/CT scan
	Assess safety/tolerability	Percentage of patients who incurred grade 3 or 4 adverse events (AEs) or serious adverse events (SAE) or AEs causing dose interruption/reduction

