### **3 STUDY IMPLEMENTATION**

#### **3.1 STUDY DESIGN**

Calcitriol (half-life is 5-8 hour) and phosphorous will be withheld for 3 days prior to the initiation of BGJ398 to allow for washout.

After initiation of study drug, subject will complete 24 weeks of BGJ398 with escalation/de-escalation of drug as described in Sections 3.1.2 and 3.3. Patients will return to the NIH every 4 weeks while on BGJ398 for an outpatient visit and labs per the schedule of events. Between monthly NIH visits, labs will be obtained per the schedule of events at the patients' local laboratories and results will be forwarded to the study team for review. In addition, any patient taking a concomitant medication associated with prolonged QT will obtain an EKG as an outpatient within 7-10 days after an increase in BGJ398 or the relevant concomitant medication. At the end of 24th week of BGJ398 treatment, subjects will be admitted as inpatients at the NIH for detailed laboratory and imaging evaluation as described in schedule of events. At the completion of the 24 weeks of treatment, patients who appear to have had a complete metabolic response will be evaluated at the NIH every 4 weeks for 3 additional visits. Complete metabolic response will be defined as normalization of blood phosphate and FGF23 levels after withdrawal of study drug. Local labs will be obtained in between NIH visits as clinically indicated on an as-needed basis. Subjects who have normal phosphate levels while on BGJ398 but have not had a complete metabolic response at the end of the 24 weeks of study drug may be considered for drug continuation in the extension phase, described in 3.1.3. Those who have not responded, have experienced significant side effects, or do not want to continue in the extension phase, will be terminated from the study and referred for other treatment.

During the active drug study period, subjects will not receive calcitriol and phosphorous supplements. However, subjects may be placed on calcitriol and phosphorous while in the post-BGJ398 drug monitoring phase or during dose interruptions, as clinically indicated. During the post-drug monitoring period calcitriol and phosphorous will be re-started on individual basis as clinically indicated (muscle weakness, bone pain, hypophosphatemia).

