### **6.3.3.2 Evaluation of Non-Target Lesions**

Complete Response (CR): Normal FGF23 and phosphorous levels off drug are considered as complete metabolic response (CR).

Non-CR/Non-PD: Off drug decrease in FGF23 levels by 50% but still greater than the upper limit of the normal range and increase in plasma phosphorous levels by 50% but not to the normal range is considered as partial metabolic response.

Progressive Disease (PD): Increase in FGF23 levels, and decreased phosphorous levels (compared to that of baseline), off the drug is considered a progressive disease.

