### **6.3.3.3 Evaluation of Best Overall Response**

Best overall response is determined in terms of FGF23 levels and blood phosphorous levels at the end of 9 months (6 months on drug and 3 months off the drug).

Complete Response (CR): Normal FGF23 and phosphorous levels are considered as complete metabolic response (CR).

Non-CR/Non-PD: Off drug decrease in FGF23 levels by 50% but still greater than the upper limit of the normal range and increase in plasma phosphorous levels by 50% but not to the normal range is considered as partial metabolic response.

Progressive Disease (PD): Increase in FGF23 levels, and decreased phosphorous levels (compared to that of baseline), off the drug is considered a progressive disease.

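### Section 8.4 and sections 6.3.3.2/6.3.3.3 define partial response differently for the same month-9 visit, and 8.4 reports an off-drug endpoint at visits scheduled on drug

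*Combined protocol and SAP*

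**What the plan says.** **Partial response, section 8.4.** The rule is "partial response defined as both a decrease of at least 50% in FGF23 and an increase of at least 50% in phosphorus". It applies at the bi-weekly visits and at the 12-week follow-up, and the follow-up rate is the one singled out for attention.

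**Partial response, sections 6.3.3.2 and 6.3.3.3.** Both use the same words. The FGF23 part is "Off drug decrease in FGF23 levels by 50% but still greater than the upper limit of the normal range". The phosphorus part is "increase in plasma phosphorous levels by 50% but not to the normal range is considered as partial metabolic response". Section 6.3.3.3 fixes the time: "Best overall response is determined in terms of FGF23 levels and blood phosphorous levels at the end of 9 months", made up of 6 months on drug and 3 months off.

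**Complete metabolic response.** Table 1 in section 1.1.2 gives "Normalization of blood phosphate and FGF23 off study drug". Section 3.1 says "Complete metabolic response will be defined as normalization of blood phosphate and FGF23 levels after withdrawal of study drug". Section 6.3.3.2 also includes the off-drug condition. Section 8.3 takes the primary endpoint at the close of the 12-week follow-up as both analytes normal, without repeating that condition. Section 8.4 then lists "Complete metabolic response rate at the bi-weekly visits" as a secondary endpoint.

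**Re-treatment.** Under sections 3.1.3 and 6.3.4, a patient without complete response after the one-week washout, or who loses it during follow-up, may be offered the extension. Section 3.1.3 limits this to patients whose phosphate normalised on BGJ398 and has them monitored monthly. Sections 8.3 and 8.4 do not say how such a patient is counted at week 36.

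**The concern.** One term carries two rules at one visit, and that visit is the main time point of a named secondary endpoint. A programmer working from 8.4 and a clinician classifying patients from 6.3.3.3 would disagree about the same patient. With ten patients, choosing between the rules after the data are seen would be post hoc.

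The label raises a second problem. Normal values during dosing show that the drug is acting. Normal values after withdrawal are the result that the primary objective is after. Section 8.4 puts both under the name complete metabolic response, so a reader of the results could take an on-drug rate for the off-drug one.

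Third, the wording of 8.3 and 8.4 leaves open whether a patient back on BGJ398 at week 36 may count as a responder. This reaches the primary endpoint as well as the secondary rates.

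**Working it through.** **1. The plan's own figures.** Table 8.4 gives exact binomial limits. With the lower limit as the 0.025 quantile of Beta(x, n−x+1) and the upper as the 0.975 quantile of Beta(x+1, n−x), N=10 gives:

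| Responders | Computed (%) | Table 8.4 (%) |
|---|---|---|
| 4/10 | 12.16 to 73.76 | 12.2 to 73.8 |
| 5/10 | 18.71 to 81.29 | 18.7 to 81.3 |
| 6/10 | 26.24 to 87.84 | 26.2 to 87.8 |

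All 11 rows at N=10 agree. The table is not in dispute; it is used only for scale in step 6.

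**2. Same visit.** 24 weeks of treatment + 12 weeks of follow-up = week 36. Section 6.3.3.3 has 6 + 3 = 9 months. Both point to the same visit.

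**3. The two rules applied to the same patients.** Let f be FGF23 in multiples of ULN and p phosphorus in multiples of LLN, with 0 for baseline and 1 for the visit. The 50% in 6.3.3 is read as at least 50%, and phosphorus at or above LLN as normal.

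- 8.4: f1 ≤ 0.5·f0 and p1 ≥ 1.5·p0.
- 6.3.3: the same two conditions, plus off drug, f1 > 1 and p1 < 1.

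The off-drug patients below are illustrative.

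| FGF23 (× ULN) | Phosphorus (× LLN) | 8.4 | 6.3.3 |
|---|---|---|---|
| 4 to 1.6 (−60%) | 0.60 to 0.92 (+53.3%) | PR | PR |
| 4 to 1.6 (−60%) | 0.60 to 1.00 (+66.7%) | PR | unclassified |
| 4 to 0.9 (−77.5%) | 0.60 to 0.95 (+58.3%) | PR | unclassified |
| 4 to 0.9 (−77.5%) | 0.60 to 1.10 (+83.3%) | CR | CR |

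The rules agree when both analytes stay abnormal or both normalise. They disagree when exactly one normalises. The second patient has a better phosphorus result than the first, yet under 6.3.3 drops from partial response to no category.

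**4. When the 6.3.3 rule cannot be met.** It needs 1.5·p0 ≤ p1 < 1, so p0 < 2/3. It also needs 1 < f1 ≤ 0.5·f0, so f0 > 2. With baseline phosphorus at or above two thirds of LLN, or baseline FGF23 at or below 2 × ULN, no outcome is a 6.3.3 partial response. Under 8.4 it remains possible. For example, at p0 = 0.70 the 50% rise is reached at 1.5 × 0.70 = 1.05 × LLN, already in the normal range.

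**5. The bi-weekly visits.** Section 3.1.2 plans continuous dosing for six 28-day cycles: 6 × 28 = 168 days = 24 weeks. The Mayo FGF23 row of the schedule of events is marked every 2 weeks from week 2 to week 24 (12 visits), then only at weeks 28, 32 and 36. Of the 12, weeks 2 to 22 (11 visits) are scheduled during treatment. Week 24 is the boundary, since section 3.4 begins sampling after the last dose. Section 3.1 agrees: off-drug visits are every 4 weeks, with local laboratory tests between them only as needed.

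**6. Scale.** One patient in ten is 1/10 = 10 percentage points. In Table 8.4, going from 4 to 5 responders moves the lower limit from 12.2% to 18.7%, or 6.5 points. This shows the table's sensitivity and does not forecast how many patients are affected.

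**The case against.** The strongest reply is that 8.4 carries its own complete rule for the only partial-response rate that section 8 plans, and that section 8 plans no best-overall-response analysis. On that view 6.3.3.3 is background. This limits the consequence: two reported counts are possible, not certain. It does not remove the conflict, because 6.3.3.3 still classifies the same patients at the same visit by a different rule.

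It can also be said that few partial responders will be off drug at week 36. Section 3.1 says that "patients who appear to have had a complete metabolic response will be evaluated at the NIH every 4 weeks for 3 additional visits"; the others are offered the extension, referred or taken off study. That stands and keeps the off-drug disagreement small.

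On labelling, the words bi-weekly visits may already signal treatment-period rates, and the complete-response sentence in 6.3.3.3 omits the off-drug condition. But its month-9 timing implies off drug, and three other places state it.

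A reader might infer more than the documents support:

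- *That re-treated patients will inflate the week-36 rates by a known amount.* No count is given or derivable. The Précis and 6.3.3.3 describe follow-up as off drug, and the monthly extension laboratory tests do not name FGF23, so status could be missing and hence a failure. Only the absence of a rule is established.
- *That weeks 2 to 22 are on drug and weeks 28 to 36 off drug for everyone.* This is true of the schedule only. Interruptions, permanent discontinuation and resumption before week 36 are all provided for.
- *That patients whose phosphorus normalises with a rise under 50%, while FGF23 stays high, are misclassified.* Both sections treat them alike, as not partial responders. That is a choice of threshold, not a contradiction.

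**Conclusion.** The point holds. Sections 8.4 and 6.3.3.2/6.3.3.3 contradict each other on partial response at the 12-week follow-up visit, for every patient who meets both 50% changes and normalises exactly one analyte. Section 8.4 also applies the name of an off-drug endpoint to visits scheduled during continuous treatment.

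The effect falls mainly on secondary response rates. It would be wrong to call the primary endpoint wholly clear of the matter: 8.3 has no off-drug clause, so read literally a patient normal on resumed BGJ398 could count as a complete response there, as such a patient could count as a partial response under 8.4. Table 1 and section 3.1 point the other way, so this is an omission to close and not evidence of a faulty primary analysis.

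The impact is modest and of unknown size: 10 points per affected patient at N=10, with no basis in the documents for the number. FGF23 and phosphorus are also analysed as continuous measures under 8.4, which limits the loss. The classification results assume that the 50% in 6.3.3 means at least 50%. The visit count rests on the one surviving FGF23 row of an incomplete calendar, supported by sections 3.1 and 3.1.2.

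**What to change.** Before analysis:

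- **One definition.** Use the same partial-response rule in 6.3.3.2, 6.3.3.3 and 8.4, for example: *not CR, FGF23 reduced by at least 50% and phosphorus increased by at least 50% from baseline*. Without the caps, patients who normalise one analyte have a category.
- **Status from actual dosing.** Derive on- or off-drug status for each patient at each visit from interruptions, discontinuation, resumption, and whether the week-24 sample was taken before or after withdrawal. Do not use fixed week labels.
- **Separate names.** Report on-drug rates as on-treatment biochemical normalization, and keep complete metabolic response for off-drug assessments.
- **Re-treated patients.** State in 8.3 and 8.4 that a patient who has resumed BGJ398 is a non-responder for off-drug complete and partial response at every later follow-up visit, including week 36. Say that this also clarifies the primary endpoint.

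The cost is protocol and SAP wording and one derived variable, with no new visits or samples. The downside is that the week-36 rates may be slightly less favourable once re-treated patients are excluded.

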### 3.4 END OF STUDY PHARMACODYNAMICS:

After the last dose is administered (24-week timepoint), the subject will be seen at the NIH and following labs will be done daily ( $\pm$  1 day) for up to 7 draws to evaluate for end-of-study pharmacodynamics.

- Blood FGF23
- Blood 1, 25 (OH)2-Vitamin D
- Blood Phosphorous, Calcium, and Creatinine
- Blood PTH
- Urine Calcium, Creatinine, and Phosphorous.

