### **6.3.4 Duration of Response**

Duration of overall response: If complete metabolic response is achieved at the end of the 1 week end-of-study pharmacodynamic period (see section 3.4) following 24 weeks of BGJ398, the subjects will be followed for an additional 11 weeks ( $\pm$  2 weeks). If the subject has not had complete metabolic response at the end the 1 week end-of-study pharmacodynamic period or at any time during the follow-up, he/she will be offered the option of entering the extension phase or referred for alternative treatments.

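### The combined complete-plus-partial response rate is read mainly at week 36, but the follow-up rules keep essentially only complete responders off drug until then

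*Combined protocol and SAP*

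**What the plan says.** **The endpoint.** Section 8.4 states: "The combined complete and partial response rate will be summarized as percent with its exact 95% confidence limits". The timing is every "bi-weekly visit but with the 12-week follow-up visit rate of primary interest". A subject without a response status is scored as a failure, whatever the reason. Section 8.4 has "partial response defined as both a decrease of at least 50% in FGF23 and an increase of at least 50% in phosphorus", and does not say whether the subject must be off drug. Sections 6.3.3.2 and 6.3.3.3 do say so: "Off drug decrease in FGF23 levels by 50% but still greater than the upper limit of the normal range", with a matching condition on phosphorus. Section 6.3.3.3 sets best overall response "at the end of 9 months (6 months on drug and 3 months off the drug".

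**Who is followed off drug.** Section 3.1 says that "patients who appear to have had a complete metabolic response will be evaluated at the NIH every 4 weeks for 3 additional visits". Subjects with normal phosphate on drug but no complete response may be considered for the extension. Those who have not responded, had significant side effects or do not want the extension leave the study. Section 3.1.3 applies at the end of the one-week period or at any time in follow-up, and offers resumed BGJ398 if phosphate had normalized on drug. Section 6.3.4 uses the same trigger: "he/she will be offered the option of entering the extension phase or referred for alternative treatments".

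**Text without that restriction.** The Précis describes three months of off-drug follow-up for the study as a whole. The calendar (3.6.1) lists FGF23 at weeks 28, 32 and 36 with no condition on response.

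**Off-drug sampling before the split.** Section 3.4: "After the last dose is administered (24-week timepoint), the subject will be seen at the NIH". Daily labs follow, up to 7 draws, including FGF23 and phosphorus. Section 8.4 does not name this period as a response time.

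**The concern.** A combined rate is there to credit benefit that falls short of complete response. At the visit that 8.4 weights most, the subjects who could earn that credit have, under the exit rules, mostly resumed drug or left. The headline combined rate then repeats the primary endpoint. Alternatively, if extension labs are used, it blends off-drug and on-drug values under one label, and the choice is left to whoever runs the analysis. The partial and progressive categories at month 9 in 6.3.3.3 have the same problem, since neither kind of subject is in complete response.

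**Working it through.** The point is mainly logical, so the check traces each subject from week 24 to week 36. The arithmetic only sizes it.

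**1. The plan's own figures.** Table 8.4 gives exact binomial (Clopper-Pearson) limits: lower = Beta quantile 0.025 with parameters (x, n−x+1), upper = Beta quantile 0.975 with parameters (x+1, n−x). For 5/10 this gives 18.7 to 81.3, and for 6/10 it gives 26.2 to 87.8, both as printed. All 21 rows reproduce within 0.1 percentage point.

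**2. Who can raise the combined rate above the complete rate.** Only a subject who is in partial but not complete response. Under either definition of partial response, that subject meets the trigger in 3.1.3 and 6.3.4.

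**3. Paths to week 36 under the exit rules.**
- Partial at one week off drug, phosphate had normalized on drug: the extension is offered. If accepted, week-36 values are on drug.
- Partial at one week, extension declined or not available: termination (3.1) or referral (6.3.4). With no week-36 value, the subject is scored as a failure.
- Complete at one week, partial at a check before week 36: the same exit, at that later time.
- Complete at every check, first partial at week 36: counted as an off-drug partial response. This is the only scheduled route.

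**4. Size.** Let C be the number in complete response at week 36, S the number who first slip to partial at that visit, and q the number who left off-drug follow-up but would still have been in partial response at week 36.
- Off-drug combined rate under the exit rules: (C + S)/N.
- Rate had the q subjects stayed under off-drug observation: (C + S + q)/N.
- Difference: q/N. With N=10, that is 10 percentage points per subject; with the fallback N=9, 1/9 = 11.1 points.

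The documents give no partial response rate, so C and q below are assumed, with S = 0. Both columns refer to week 36, and the limits are those of Table 8.4.

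| C | q | Under exit rules | If the q subjects had stayed |
|---|---|---|---|
| 0 | 3 | 0% (0 to 30.8) | 30% (6.7 to 65.3) |
| 4 | 1 | 40% (12.2 to 73.8) | 50% (18.7 to 81.3) |
| 4 | 2 | 40% (12.2 to 73.8) | 60% (26.2 to 87.8) |
| 4 | 3 | 40% (12.2 to 73.8) | 70% (34.8 to 93.3) |
| 6 | 2 | 60% (26.2 to 87.8) | 80% (44.4 to 97.5) |

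**5. On-drug values.** Extension subjects have monthly labs (3.1.3), and the partial definition in 8.4 has no off-drug condition. With C = 4 and three extension subjects who meet that definition on drug, the week-36 rate is 4/10 = 40% if their values are excluded and 7/10 = 70% if they are counted. The text permits either.

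**The case against.** The strongest reply is that the exit is less firm than the trace assumes. Section 3.1 says such subjects may be considered for the extension, and 3.1.3 offers it only if phosphate normalized on drug. Referral in 6.3.4 does not itself say that observation ends. Section 3.1 also allows calcitriol and phosphorus for hypophosphatemia during post-drug monitoring, which suggests that some subjects without complete response stay under observation. The Précis and calendar carry no restriction. This stands in part: the documents conflict about who is followed. But none of this text says that partial responders remain off drug and observed to week 36, whereas 3.1, 3.1.3 and 6.3.4 direct them elsewhere.

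A second reply is that 8.4 never requires off-drug values, so a week-36 reading could exist for extension subjects. That is true, and it is the other half of the problem: it would mix on-drug with off-drug response without saying so.

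A reader might also infer more than the documents support:
- That every partial responder is removed after one week. Subjects who lose complete response later leave later, and the conflicting text above rules out *every*.
- That the trial cannot study partial response, or that lasting partial benefit would look like none. The combined rate is also reported at the bi-weekly visits, and off-drug FGF23 and phosphorus are collected in 3.4. Only the headline week-36 rate is uninformative.
- That the rate at one week set against the rate at week 36 measures the loss. Some partial responders could relapse by week 36 even if kept off drug.

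Finally, this is one of eight listed secondary endpoints in a single-arm study of 10, with no test or decision rule attached to it. That limits the importance of the point but does not remove it.

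**Conclusion.** The conflict is real. If the exit rules are followed, the week-36 combined rate is essentially the complete-response rate, apart from a complete responder who first slips at that visit. If extension labs are counted, it is a mix of off-drug and on-drug values. The shortfall is q/N, or 10 percentage points per subject at N=10, for those who left and would still have been in partial response; q cannot be taken from the documents.

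The conclusion rests on reading 3.1, 3.1.3 and 6.3.4 as governing over the unrestricted follow-up in the Précis and calendar. If the sponsor's intention is to observe every subject off drug to week 36, the reading in 8.4 can stand, but those three sections then contradict it. The primary endpoint is not affected, because a partial responder is a failure there in any case. Table 8.4 is also unaffected. The wording should be corrected; the design is not otherwise called into question.

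**What to change.** - In 8.4 and 6.3.3.3, make the main off-drug reading of the combined rate, and of the partial and progressive categories, the last available draw of the one-week off-drug period in 3.4. It is taken before subjects are split. Because 3.4 allows up to 7 draws, each within a day, define *last available* and report the days off drug.
- Keep week 36 as a supplementary reading, labelled as reflecting essentially complete responders only.
- State in 8.4 that values taken on resumed BGJ398 do not count as off-drug response. If they are shown at all, show them separately.
- Reconcile the Précis, the calendar and Sections 3.1, 3.1.3 and 6.3.4 on who is followed off drug and for how long. Which rule is right is a clinical decision for the sponsor and investigators.

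The cost is wording only: no new visits, samples or treatment rules. The downside is that one week off drug shows short-term, not lasting, partial response. Durability is still covered for complete responders by the week-36 primary endpoint.

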### 1.2 BACKGROUND AND RATIONALE

Tumor-induced osteomalacia (TIO) is a rare neoplastic syndrome that is associated with fractures, bone pain, and muscle weakness (*1*). The vast majority of cases are caused by fibroblast growth

*Abbreviated Title: BGJ398 in TIO*

*Version Date: 21MAY2019*

factor-23 (FGF23)-secreting mixed connective tissue mesenchymal tumors. FGF23 acts by binding to target cells via an FGF receptor (FGFR1), but signaling requires the co-receptor Klotho (2). Activation of FGFR1 leads to inhibition of sodium-phosphate co-transporters in the proximal tubule cells, resulting in decreased tubular phosphate reabsorption, increased renal phosphate excretion, and hypophosphatemia (3). In addition, FGF23 downregulates  $1\alpha$ -hydroxylase and up-regulates 24-hydroxylase, resulting in decreased production of the active form of vitamin D, 1, 25-dihydroxy vitamin D, further contributing to hypophosphatemia. While tumor resection can cure TIO, tumors are typically small (often < 2 cm) and notoriously difficult to locate. Medical treatment of patients whose tumors cannot be located, or are inoperable or widely metastatic, is difficult. It involves at least thrice daily phosphate, which is poorly tolerated due to diarrhea, and active vitamin D. Frequent monitoring with careful adjustment of medications is required to prevent untoward effects of medical therapy, including secondary/tertiary hyperparathyroidism hypercalcemia, hypercalciuria, nephrocalcinosis, and nephrolithiasis.

Recently, translocations resulting in a fibronectin-fibroblast growth factor receptor-1 (FN1/FGFR1) fusion gene were identified in 40-60% of the tumors investigated, suggesting a driver role for FGFR1 signaling in TIO tumorigenesis (4, 5). Thus, it was hypothesized that an FGFR inhibitor may be effective therapy and possibly tumoricidal in TIO.

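### The 1,25-(OH)2-vitamin D contrasts compare a calcitriol-free baseline with later values that may be taken on calcitriol, with no rule in section 8.4 to flag them

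*Combined protocol and SAP*

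**What the plan says.** **The endpoint.** Section 1.2 explains why the analyte matters: FGF23 leads to "decreased production of the active form of vitamin D, 1, 25-dihydroxy vitamin D". A rise is therefore meant to show that FGF23 action has fallen. Section 8.4 lists "the increase in both plasma phosphorus and 1,25-OH 2 -vitamin D" among the changes of primary interest in the biochemical measures.

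**The analysis.** These measures are "analyzed using repeated measures mixed models with the contrast of primary interest between the baseline and the 12-week follow-up visit". Section 8.4 adds: "Additional post hoc comparisons with corrections for multiple comparisons will compare the measures at the end of each cycle to baseline".

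**Calcitriol before and during treatment.** Section 3.1 states: "Calcitriol (half-life is 5-8 hour) and phosphorous will be withheld for 3 days prior to the initiation of BGJ398 to allow for washout". It continues: "During the active drug study period, subjects will not receive calcitriol and phosphorous supplements".

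**Calcitriol afterwards.** The same section provides that "subjects may be placed on calcitriol and phosphorous while in the post-BGJ398 drug monitoring phase or during dose interruptions, as clinically indicated". For follow-up it adds: "During the post-drug monitoring period calcitriol and phosphorous will be re-started on individual basis as clinically indicated (muscle weakness, bone pain, hypophosphatemia").

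**Data handling.** Section 8.4 covers log transformation, absent baseline values, and other missing values through restricted maximum likelihood. It says nothing about values obtained on calcitriol. Section 4 requires concomitant medications to be entered on a form in the eCRF.

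**The concern.** A value measured on calcitriol is not missing, so under section 8.4 it enters the model as an ordinary observation. The two ends of the contrast are then not alike. Baseline is protected by a washout, while no calcitriol-free interval is required before any later sample.

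The direction is the awkward part. Calcitriol adds to the later value only, so it pushes the change from baseline upward, which is the change the plan hopes to see. The restart triggers in section 3.1 are signs of returning or persisting disease, so a patient who is doing poorly could contribute a rise. The effect on mineral homeostasis, a secondary objective (section 1.1.2, Table 1), would then partly reflect the supplement.

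**Working it through.** The plan states no effect size, standard deviation or power for this analyte, so there is no figure of its own to reproduce. The check has four steps.

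**1. Is baseline free of calcitriol?** Inputs from section 3.1: half-life 5 to 8 hours; 3 days = 72 hours. Fraction remaining = 0.5^(hours / half-life).

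- Half-life 5 h: 72/5 = 14.4 half-lives; 0.5^14.4 = 0.005%.
- Half-life 8 h: 72/8 = 9 half-lives; 0.5^9 = 0.20%.

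Baseline is effectively clean.

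**2. What if a later sample has no washout?** The same formula gives the fraction of a dose remaining:

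| Hours since dose | Half-life 5 h | Half-life 8 h |
|---|---|---|
| 4 | 57% | 71% |
| 12 | 19% | 35% |
| 24 | 3.6% | 12.5% |

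A sample on the day of a dose can carry a substantial supplement component.

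**3. Which visits are exposed?**

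- *Week 36, the main contrast:* inside the post-drug phase, so calcitriol is allowed.
- *Cycle-end visits on drug:* not exposed, because calcitriol is barred.
- *Cycle-end visits in a dose interruption:* exposed if calcitriol was restarted.

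**4. How large could the bias be?** The documents give neither the rise that calcitriol causes nor the number who would take it, so both are assumed. Suppose BGJ398 has no true effect, and k of m patients at a visit have their level multiplied by R. On the log scale the spurious geometric mean ratio is R^(k/m). This is for simple observed means; the mixed model would also draw on other visits.

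For m at week 36, section 8.5 hypothesises effectiveness in 40-60% of 10 patients, that is 4 to 6, if only these stay in follow-up. With one patient on calcitriol:

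| Patients at the visit | R = 1.3 | R = 1.5 | R = 2.0 |
|---|---|---|---|
| 4 | +6.8% | +10.7% | +18.9% |
| 5 | +5.4% | +8.4% | +14.9% |
| 6 | +4.5% | +7.0% | +12.2% |
| 10 (cycle-end visit) | +2.7% | +4.1% | +7.2% |

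For example, 1.3^(1/5) = 1.054 and 2.0^(1/5) = 1.149.

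**The case against.** **Few patients at week 36 should be on calcitriol.** Section 3.1 schedules the follow-up visits for patients who appear to be complete responders. Under sections 3.1.3 and 6.3.4, a patient who loses that response is offered the extension phase or referred elsewhere. Someone restarted for hypophosphatemia would normally leave follow-up. This stands, and it rules out sizing the problem as several of ten patients at week 36. It does not remove the problem: muscle weakness and bone pain are also triggers, so a patient with normal phosphate can be restarted, and the denominator shrinks with the numerator.

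**On-treatment exposure is narrow.** It needs an interruption, a calcitriol restart, and a sample before the calcitriol has cleared. The parallel per-protocol analysis (sections 8.1 and 8.4) also removes patients who received less than 65% of drug in a cycle. In 28 days, missing 10 leaves 18/28 = 64%, which fails; missing 9 leaves 19/28 = 68%, which passes. This is a partial safeguard. Shorter interruptions and all follow-up use remain.

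**Exclusion can mislead in the same direction.** This stands. Suppose, by assumption, that four of five patients are truly at 1.5 times baseline and one relapser is at 1.0:

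- True ratio: 1.5^0.8 = 1.38.
- Keeping the relapser's value, raised 1.3 to 2.0 times by calcitriol: 1.38 × 1.054 = 1.46 to 1.38 × 1.149 = 1.59.
- Dropping it: 1.50, about 8% too high (1.50/1.383 = 1.084).

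Neither result alone is safe, so exclusion should not be the only analysis.

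**The analyte is not singled out.** The sentence on primary interest in section 8.4 also covers FGF23, phosphorus and the other parameters, and Table 1 calls the measure secondary/exploratory. This limits the weight of the point.

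**Conclusion.** The point holds as a modest gap in the analysis plan. Followed as written, section 8.4 compares a supplement-free baseline with values that may include supplement, and the error favours the hypothesised increase. It concerns the continuous 1,25-(OH)2-vitamin D measure at post-drug visits, including the 12-week visit of the main contrast, and at any cycle-end visit during an interruption.

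The size is illustrative only: +5% to +15% if one of five patients is on calcitriol and it raises the level by 30% to 100%. The number affected is probably small. The point also rests on calcitriol being the assayed hormone. That is basic pharmacology, and it fits section 1.2, which calls 1,25-dihydroxy vitamin D the active form and names active vitamin D as standard treatment, with section 4.2.4, where that treatment is calcitriol.

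A reader might infer more, and the documents do not support it:

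- *That the assay then measures only the supplement.* It reads endogenous and supplemental hormone together and cannot separate them.
- *That all cycle-end contrasts are contaminated.* Outside interruptions, calcitriol is not given during active treatment.
- *That the primary result is affected through this analyte.* Section 8.3 defines complete response by FGF23 and phosphorus.

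**What to change.** Add to section 8.4, for 1,25-(OH)2-vitamin D:

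1. Flag each value taken within 3 days of a calcitriol dose, using the concomitant-medication form with calcitriol start and stop dates. The 3 days are the protocol's own washout interval.
2. Report the model contrasts both with and without flagged values.
3. List, by patient, all values with flag, visit and drug status.
4. Do not attribute a rise to BGJ398 unless it also holds without the flagged values.

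State the limitation in the same place. Exclusion loses a few values and is informative, because a restart may follow relapse. The analysis without flagged values may therefore be too favourable and must be read with the listing.

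The cost is a short SAP addition, a derived flag and one extra model run. Section 4 does not say that start and stop dates are captured, so the form should be checked and those fields added if absent. The rule should be fixed before results are seen, since with so few patients a later choice of values could decide the finding. No change to when calcitriol is given is proposed.
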